4.9 Criteria for Removal from Study Treatment

Patients will be removed from study treatment when any of the criteria listed below applies. The reason for study treatment removal and the date the patient was removed must be documented in the Case Report Form.

A subject must be discontinued from the trial for any of the following reasons:

- The subject or legal representative (such as a parent or legal guardian) withdraws consent, or
- Patient is lost to follow-up.

A subject must be discontinued from treatment (but may continue to be monitored in the post-treatment follow-up portion of the trial) for any of the following reasons:

- The subject or legal representative (such as a parent or legal guardian) withdraws consent for treatment,
- Development of distant metastatic disease,
- Intercurrent illness that prevents further administration of treatment,
- Dose-limiting toxicities with exceptions to treatment discontinuation as described in **Section 4.6**,
- Fulfilling criteria for permanent discontinuation of BMS-813160 (see **Section 5.2.6.2**),

A Phase I/II trial of combination immunotherapy with nivolumab and a CCR2/CCR5 dual antagonist (BMS-813160) with or without GVAX following chemotherapy and radiotherapy for locally advanced pancreatic ductal adenocarcinomas (PDACs)

- Unacceptable toxicity/toxicities with exceptions to treatment discontinuation as described in **Section 4.7**,
- Need for >2 dose delays due to the same toxicity as per the dose delay guidelines (see **Section 5.1**),
- If any one or more of the study drugs (nivolumab, BMS-813160 and/or GVAX) are discontinued,
- Inability to reduce corticosteroid dose for immune-related adverse reactions to ≤ 10 mg prednisone or equivalent per day,
- Any dosing delay lasting > 28 days will be cause for permanent discontinuation. Extensions to the period of dose delays may be granted for individual participants on a case-by-case basis after specific consultation and agreement between Principal Investigator, IND Sponsor and BMS in settings where benefit/risk may justify continued study treatment (e.g. participant deriving clinical benefit who requires prolonged steroid taper for management of non-DLT immune-related AEs or experiences delays for management of a non-drug-related AE).
 - Accordingly, dosing delays to allow for prolonged steroid tapers to manage drug-related AEs are allowed. Additionally, dosing delays > 28 days that occur for non-drug-related reasons may be allowed if approved by the Principal Investigator, IND Sponsor, and BMS.
 - Prior to re-initiating treatment in a participant with a dosing delay lasting > 28 days, the Principal Investigator, IND Sponsor and BMS must be consulted.
 - Tumor assessments should continue as per protocol even if dosing is delayed.
- Investigator's decision to withdraw the subject (the IND Sponsor and BMS should be included in this decision),
- If in the opinion of the Investigator, a change or temporal or permanent discontinuation of therapy would be in the best interest of the patient. The IND Sponsor should be included in this decision,
- Noncompliance with trial treatment or procedure requirements,
- Patient is lost to follow-up, or
- Patient becomes pregnant.

4.10 End of Treatment (EOT)

All subjects will return to the study site 30 days (± 7 days) after the last dose of study drug (or within 7 days prior to initiation of a new anti-cancer treatment, whichever comes first) for an EOT evaluation. Procedures and assessments performed at this visit and beyond should follow the respective guidelines described in **Sections 4.11 and 9** as appropriate.

A Phase I/II trial of combination immunotherapy with nivolumab and a CCR2/CCR5 dual antagonist (BMS-813160) with or without GVAX following chemotherapy and radiotherapy for locally advanced pancreatic ductal adenocarcinomas (PDACs)

4.11 Duration of Follow-up

4.11.1 Safety Follow-up

Subjects who discontinue treatment should be contacted by telephone or email at 100 days (+ 14-day reporting window) from their last dose of study drug or within 7 days before initiation of a new antineoplastic treatment (whichever comes first) to assess for treatment related toxicities. In addition, all SAEs occurring during this time should be reported as well.

Subjects who are discontinued from the study treatment due to an unacceptable drug-related AE will be monitored for safety until the resolution of the AE to \leq grade 1 or stabilization or until initiation of a new therapy for their cancer, whichever occurs first.

4.11.2 Clinical Follow-up

All enrolled subjects who discontinue treatment without disease progression will enter the clinical follow-up portion of the trial. Subjects will begin the clinical follow-up period after they complete the EOT visit. Clinical follow-up visits will occur every 12 weeks (\pm 2 weeks) until: 1) start of a new antineoplastic therapy (information of the new cancer therapy will be collected), 2) disease progression, 3) death, 4) withdrawal of consent, or 5) study closure, whichever occurs first. Refer to **Section 9** for the schedule of assessments that should be performed at each visit. After disease progression or start of a new antineoplastic therapy, subjects will enter the survival follow-up portion of the trial (**Section 4.11.3**).

4.11.3 Survival Follow-up

Subjects who discontinue treatment and have disease progression or start a new antineoplastic therapy will enter the survival follow-up portion of the trial. Subjects should be contacted every 12 weeks (\pm 2 weeks) to monitor overall survival. Information of other cancer therapies after discontinuation from the study treatment will be collected as well.

5. DOSING DELAYS/DOSE MODIFICATIONS

[figure not shown]
5.1 Dose Delays

All scheduled cycles within a course are to be given approximately four weeks apart. If necessary, a cycle may be delayed for up to one week, and subsequent cycles should continue to be four weeks apart. If delayed more than one week, the Principal Investigator must be contacted for further instructions on continued treatment. Additional delays or modifications to the treatment schedule must be approved by the Principal Investigator or IND Sponsor.

A Phase I/II trial of combination immunotherapy with nivolumab and a CCR2/CCR5 dual antagonist (BMS-813160) with or without GVAX following chemotherapy and radiotherapy for locally advanced pancreatic ductal adenocarcinomas (PDACs)

If a delay occurs between Day 1 and 2 of a cycle:

- Nivolumab-related infusion reactions must resolve to baseline prior to administration of GVAX and BMS-813160.
- GVAX and BMS-813160 treatment and assessments can be resumed after the reason for delay has resolved.

5.2 Dose Modifications

Participants will be monitored continuously for AEs while on study therapy. Participants will be instructed to notify the study site for any and all AEs. For an AE requiring dose modification of BMS-813160, the other study treatments (i.e. GVAX and nivolumab) should be interrupted to allow recovery from the AE. If there is an AE and/or reaction (i.e. infusion reaction) to GVAX or nivolumab, all study treatments will be interrupted to allow recovery from the reaction.

All participants who discontinue study treatment should comply with protocol-specified follow-up procedures as outlined in **Section 4.11**. The only exception to this requirement is

A Phase I/II trial of combination immunotherapy with nivolumab and a CCR2/CCR5 dual antagonist (BMS-813160) with or without GVAX following chemotherapy and radiotherapy for locally advanced pancreatic ductal adenocarcinomas (PDACs)

when a participant withdraws consent for all study procedures including post-treatment study follow-up or loses the ability to consent freely (e.g. is imprisoned or involuntarily incarcerated for the treatment of either a psychiatric or physical illness).

If study treatment is discontinued prior to the participant's completion of the study, the reason for the discontinuation must be documented in the participant's medical records and entered on the appropriate Case Report Form (CRF).

5.2.1 Nivolumab Dose Modifications

No dose modifications (increase or decrease) to Nivolumab are allowed. Doses can be delayed for side effects. If there are delays due to AEs or reactions to GVAX and/or BMS-813160, nivolumab will also be held to allow recovery from the AE/reaction.

5.2.2 GVAX Dose Modifications

No dose modifications (increase or decrease) to GVAX are allowed. Doses can be delayed for side effects. If there are delays due to AEs or reactions to nivolumab and/or BMS-813160, GVAX will also be held to allow recovery from the AE/reaction.

5.2.3 BMS-813160 Dose Modifications

Medical management for dose delay and adverse events are outlined in **Appendix E**.

5.2.3.1 Dose Reductions in BMS-813160

- 1) New onset of QTcF intervals > 500 msec or prolongation > 50 msec over baseline, new onset QRS intervals > 140 msec, new onset bundle branch block or symptomatic bradycardia, Type 2 second or third-degree heart block will require dose interruption and restarting at one dose level lower. Any electrolyte abnormalities should be corrected and ECG should be repeated with cardiology consultation if clinically indicated.
- 2) Grade 3 non-hematologic toxicity or Grade 4 non-hematologic toxicity attributed to BMS-813160 (that do not meet criteria for removal from study treatment, **Section 4.9**) will require one dose level reduction.
 - Any Grade 3 laboratory only abnormalities (that do not meet criteria for removal from study treatment, **Section 4.9**) without clinical manifestations or electrolyte abnormalities that may be managed with supplementation can be managed with dose delay and do not automatically need dose modification.
- 3) Participants who need a dose reduction for toxicity attributable to BMS-813160 will continue on the reduced dose of BMS-813160 for the remainder of the study.

4) BMS-813160 dose modifications are presented in **Table 3**.

5.2.3.2 Guidelines for Permanent Discontinuation of BMS-813160

Participants will be required to permanently discontinue BMS-813160 for the following reasons:

- 1) If the participant fulfils the criteria for removal from study treatment (**Section 4.9**).
- 2) If a participant needs more than 2 dose reductions of BMS-813160 for toxicity, then participant will permanently discontinue further treatment with all three study drugs and be taken off treatment, unless it is determined to be in the participant's best interest to continue as per the Principal Investigator, IND Sponsor and BMS.

Table 3: Recommended Dose Modifications for BMS-813160

	BMS-813160 dose	
Starting Dose	300 mg BID	150 mg BID
Dose Reduction 1	150 mg BID	150 mg daily
Dose Reduction 2	150 mg daily	Discontinue

6. ADVERSE EVENTS: LIST AND REPORTING REQUIREMENTS

This study will use the descriptions and grading scales found in the revised National Cancer Institute Common Terminology Criteria for Adverse Events (CTCAE) Version 5.0 for adverse event reporting that can be found at http://ctep.cancer.gov/protocolDevelopment/electronic_applications/ctc.htm.

Information about all adverse events, whether volunteered by the patient, discovered by investigator questioning, or detected through physical examination, laboratory test or other means, will be collected, recorded, and followed as appropriate.

The Principal Investigator has the primary responsibility for continuous internal monitoring for safety, protocol compliance, and identification, grading, coding, and required reporting of all anticipated and unanticipated adverse events and protocol problems. Although this responsibility is usually shared among the Principal Investigator, research nurse, and data manager, the Principal Investigator is ultimately responsible for grading and attribution of all events.

All adverse events experienced by patients will be collected and reported from the first dose of the investigational agent, throughout the study, and will only be followed for 4 weeks unless related to the investigational agent. Only toxicities considered related to study procedures or treatment will be collected from the time of surgery until the start of Cycle 2.

A Phase I/II trial of combination immunotherapy with nivolumab and a CCR2/CCR5 dual antagonist (BMS-813160) with or without GVAX following chemotherapy and radiotherapy for locally advanced pancreatic ductal adenocarcinomas (PDACs)

All Serious Adverse Events (SAEs) will be collected from the first day of immunotherapy treatment through 100 days after the end of treatment or until a new antineoplastic treatment is initiated, whichever occurs first. All SAEs whether related or not related to study drug must be reported to the IND Sponsor and BMS Worldwide Safety. If applicable, SAEs must be collected that relate to any later protocol-specified procedure (e.g. a follow-up skin biopsy).

Subjects who have an ongoing adverse event related to the study procedures and/or medication(s) may continue to be periodically contacted by a member of the study staff until the event is resolved or determined to be irreversible by the investigator.

Laboratory abnormalities: Laboratory abnormalities present at the screening visit will be recorded as pre-treatment signs and symptoms. After study treatment administration, all grade 3 and 4 clinical laboratory results that represent an increase in severity from baseline will be reported as adverse events. A grade 1 or 2 clinical laboratory abnormality should be reported as an adverse event only if it is considered clinically significant by the investigator. Any laboratory abnormality that required the participant to have a study drug discontinued or interrupted or required the participant to receive corrective therapy will be reported.

6.1 Definitions

6.1.1 Adverse Event (AE)

Adverse event is defined as any undesirable sign, symptom or medical condition occurring after starting the study drug (or therapy) even if the event is not considered to be related to the study. An undesirable medical condition can be symptoms (e.g., nausea, chest pain), signs (e.g., tachycardia, enlarged liver) or the abnormal results of an investigation (e.g., laboratory findings, electrocardiogram). Medical conditions/diseases present before starting the study treatment are only considered adverse events if they worsen after starting the study treatment (any procedures specified in the protocol). Adverse events occurring before starting the study treatment but after signing the informed consent form will not be recorded. Additionally, expected progression of the disease being studied will not be recorded as an adverse event. Abnormal laboratory values or test results constitute adverse events only if they induce clinical signs or symptoms or require therapy.

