1.7 Study Design

This is a single-center, open label, phase I/II clinical trial to evaluate the immune effects, safety and clinical activity of the combination of nivolumab and CCR2/CCR5 dual antagonist with or without GVAX in patients who have received standard chemotherapy and stereotactic body radiation therapy (SBRT) for LAPC.

Patients who have a new diagnosis of untreated LAPC will be eligible for enrollment. We will consent patients at the time of diagnosis of LAPC based upon criteria from NCCN Guidelines as determined by review of imaging and pathology at our institution. If the patient has not had a diagnostic core biopsy adequate for review by our institution, an on-study core diagnostic biopsy will be performed. If the patient's available imaging is not adequate for review by our institution, repeat imaging will be performed. The patient will also undergo blood draws at the time of screening and enrollment. After completing all screening procedures and meeting eligibility criteria, the patients will then receive FOLFIRINOX-based induction chemotherapy and SBRT. Chemotherapy and radiotherapy are considered standard therapy. Chemotherapy may be administered at any facility, but SBRT treatment will be performed at Johns Hopkins. Of note, patients should meet all eligibility criteria and have all screening procedures completed prior to initiating chemotherapy, however they may be enrolled up to one month after beginning SOC chemotherapy to allow for time to collect records from outside institutions if necessary. Only toxicities considered related to study procedures or treatment will be collected during this period. The patients should receive at least eight and no more than sixteen 14-day cycles of FOLFIRINOX-based chemotherapy. After completion of chemotherapy, the patients will undergo EUS-guided fiducial placement along with a post-chemotherapy core biopsy of the pancreas tumor, blood draws to evaluate for circulating tumor cells and other inflammatory markers and an SBRT simulation. We will not confirm presence of tumor in the post-chemotherapy core biopsy since some patients may not have persisting tumor; the biopsy is to evaluate the tumor microenvironment. SBRT will be initiated (6.6 Gy x 5 days) approximately two to four weeks after completion of chemotherapy.

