The Phase II portion is a randomized two-arm study to evaluate immune response, efficacy and safety of the combination of nivolumab and CCR2/CCR5 dual-antagonist (BMS-813160) with and without GVAX. We will be monitoring the toxicities for each arm in the Phase II portion, and if we observe >33% unacceptable toxicities in the first 6 patients or any time afterwards in any arm, we will halt the enrollment pending safety evaluations.

DLTs will be assessed in the first cycle of Phase I, starting Cycle 1 Day 1 through prior to initiation of Cycle 2. Unacceptable toxicities will be used to monitor safety from Cycle 2 Day 1 of Phase I through to end of study treatment and from Cycle 1 Day 1 of Phase II through to end of treatment. During periods of standard of care treatment (FOLFIRINOX-based chemotherapy, SBRT, Surgery) only AEs considered related to study treatment will be collected. If patients develop adverse events (AEs) to any of the three immunotherapies

A Phase I/II trial of combination immunotherapy with nivolumab and a CCR2/CCR5 dual antagonist (BMS-813160) with or without GVAX following chemotherapy and radiotherapy for locally advanced pancreatic ductal adenocarcinomas (PDACs)

(BMS-813160, nivolumab or GVAX) leading to its/their discontinuation, they will be taken off the trial.

All patients will undergo standard of care evaluations consisting of history and physical, CT of the chest/abdomen/pelvis or MRI abd/pelvis and non-contrast CT chest (if do not tolerate contrast) to evaluate for local progression and metastatic disease while they are on study.

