6.5 Reporting

6.5.1 General

All adverse events (both expected and unexpected) will be captured on the appropriate study-specific Case Report Forms (CRFs), with the exception of unrelated adverse events that occur during the standard of care treatment periods. The standard of care treatment periods include FOLFIRINOX-based chemotherapy administration and SBRT treatment through initiation of Cycle 1 of combination immunotherapy and from surgical resection or Nanoknife procedure through initiation of Cycle 2 combination immunotherapy. All AEs collected will be reported in aggregate in the final study report, which must be provided to BMS. No individual or expedited reporting is required.

All serious adverse events, regardless of causality to study drug, including those thought to be associated with protocol-specified procedures will be reported promptly to the IND Sponsor and BMS Worldwide Safety within 24 hours of recognition, with the exception of unrelated SAEs that occur during the standard of care treatment periods as defined above. Serious adverse events should be reported using the form found in **Appendix B**. If this falls on a weekend or holiday, an email notification is acceptable but must be followed by an SAE reporting form on the next business day.

SAE reports and any other relevant safety information are to be sent to:

IND Sponsor ([name]): [REDACTED]

BMS: [REDACTED]

After the initial AE or SAE report, the investigator is required to proactively follow each subject and provide further information to the safety department in regard to the subject's condition.

All AE(s) and SAE(s) will be followed until:

- Resolution

A Phase I/II trial of combination immunotherapy with nivolumab and a CCR2/CCR5 dual antagonist (BMS-813160) with or without GVAX following chemotherapy and radiotherapy for locally advanced pancreatic ductal adenocarcinomas (PDACs)

- The condition stabilizes
- The event is otherwise explained
- The subject is lost to follow-up
- Death

As soon as relevant information is available, a follow-up SAE report will be submitted to the IND Sponsor and BMS.

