8.1 Tumor Tissue Studies

4-6 core tumor biopsies will be collected during

- 1) initial study enrollment if adequate diagnostic biopsy is not available,
- 2) the scheduled endoscopy with fiducial placement and
- 3) after pre-surgical evaluation if the patient is not a surgical candidate.

The core biopsy specimens will be collected for both snap frozen specimens and FFPE slides. The core formalin samples will be placed in one FFPE tissue block.

Additional tissue will be collected during surgical resection/NanoKnife procedure if the patient is a surgical candidate. Resected PDAs will be archived for FFPE tissue slides, frozen sections and freshly isolated TILs. Detailed instructions for tissue collection, processing and shipment are provided in the procedures manual.

The patient may also have biopsies of metastases performed. Post-treatment biopsies will only be obtained if the tumor is thought to be reasonably safe to biopsy, and biopsies not obtained due to concerns for patient safety will not be considered deviations. Additional optional biopsies may be obtained later in the course of therapy. Archival tumor samples will also be collected for every patient (slides and/or blocks). Archival tumor samples will not be

A Phase I/II trial of combination immunotherapy with nivolumab and a CCR2/CCR5 dual antagonist (BMS-813160) with or without GVAX following chemotherapy and radiotherapy for locally advanced pancreatic ductal adenocarcinomas (PDACs)

collected if the biopsy was a fine needle aspiration.

These tissue samples will be banked for the evaluation of PD-L1/PD-1, their associated immune suppressive pathways and other immune activation pathways to assess the effect of treatment upon the tumor microenvironment and the correlations between these immune parameters and clinical response. Immunohistochemistry, flow cytometry, quantitative PCR assays and microarray analysis will be employed. In addition, to identify potential mutated neoepitope-specific T-cell repertoire by TCR clonality and/or the MANAFEST assay and in pre- and post-treatment tumor specimens and peripheral blood lymphocyte (PBL) over time on treatment.

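### Section 6.1.1 bars recording of events before study treatment, while Sections 1.7 and 6.5.1 collect procedure-related events from that period, so complications of the pre-treatment pancreatic biopsies fall under conflicting instructions

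*Combined protocol and SAP*

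**What the plan says.** Section 8.1 states that "4-6 core tumor biopsies will be collected during" three occasions: enrolment if the diagnostic biopsy is inadequate, the endoscopy for fiducial placement, and the post-Cycle-1 evaluation if the patient is not a surgical candidate. The first two come before any study drug. Willingness to have them is an eligibility requirement (3.1.2 and 3.1.10). The biopsy at fiducial placement follows chemotherapy and precedes SBRT, which is the time point that the Phase II immune-response endpoint uses as baseline (1.4.2).

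On events in that period, the document says the following.

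- Section 6.1.1 defines an adverse event as "any undesirable sign, symptom or medical condition occurring after starting the study drug (or therapy", and adds: "Adverse events occurring before starting the study treatment but after signing the informed consent form will not be recorded".
- Section 6 starts AE collection with the first dose of an investigational agent. For serious events: "All Serious Adverse Events (SAEs) will be collected from the first day of immunotherapy treatment through 100 days after the end of treatment".
- Section 1.7, in the paragraph on enrolment and chemotherapy: "Only toxicities considered related to study procedures or treatment will be collected during this period".
- Section 1.7, in the paragraph on DLTs and unacceptable toxicities, says of the chemotherapy, SBRT and surgery periods that "only AEs considered related to study treatment will be collected".
- Section 6.5.1 requires serious events, including those associated with protocol procedures, to be reported within 24 hours, "with the exception of unrelated SAEs that occur during the standard of care treatment periods as defined above". Its first such period ends only when Cycle 1 begins. It exempts non-serious events on the same basis.

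**The concern.** A complication of the research cores before Cycle 1 Day 1 meets an instruction not to record in one section and a duty to collect or report in two others. These biopsies are invasive, are done for the study, and are a condition of entry. The stake is participant-safety reporting: the IND sponsor, the company and the IRB should learn of harm from a procedure that patients undergo because they joined the trial. If staff resolve the conflict differently from case to case, capture will be uneven as well as incomplete.

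**Working it through.** The documents contain no figure to reproduce, so the check is textual. Take one test case: after enrolment and before Cycle 1 Day 1, a patient is admitted for more than 24 hours with a complication that the investigator attributes to the research cores. Apply each provision in turn.

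| Provision | Result for this event |
|---|---|
| 6.1.1, definition | Not an adverse event: study drug or therapy has not started |
| 6.1.1, sentence on events after consent | Not recorded; no exception for procedures |
| Section 6, AE start | Outside the collection window |
| Section 6, SAE start | Outside the window; the clause on procedures reaches only later ones |
| 1.7, enrolment and chemotherapy paragraph | Collected, as related to a study procedure |
| 1.7, DLT and toxicity paragraph | Not collected: before the first dose nothing can be related to study drug, and procedures are not mentioned |
| 6.5.1, SAE sentence | Reported within 24 hours |
| Section 9 calendar | AE evaluation scheduled at pre-immunotherapy screening, before Cycle 1 Day 1 |

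Three further steps show why 6.5.1 alone does not settle the matter.

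1. **Non-serious events.** Section 6.5.1 names procedures only in its SAE sentence. For other events it exempts whatever is unrelated.
2. **Meaning of unrelated.** Section 6.2 rates relationship to study drug only, and expects a related event to follow dosing. On that scale a biopsy complication before the first dose is unrelated, so the 6.5.1 exemption could remove it. The SAE form in Appendix B has columns for the three agents and the underlying disease, and none for a procedure.
3. **Which biopsies are affected.** The enrolment and fiducial-placement biopsies fall in the conflicting period. The EUS biopsy after Cycle 1 does not, because study drug has started by then.

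The conflict is therefore confirmed for the two pre-treatment biopsies. For serious events it lies between 6.1.1, the Section 6 start date and the second 1.7 statement on one side, and the first 1.7 statement and 6.5.1 on the other. For non-serious events, 6.2 weakens the 6.5.1 route as well.

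**The case against.** The strongest defence is that the reporting text already covers the test case. Section 6.5.1 is the specific rule and is explicit on procedure-associated serious events. The SAE definition in 6.1.2 has no start-of-treatment limit, and the same section says how to describe an SAE that is a complication of a study procedure. Section 6.5.2 sends all serious events to the IRB and IBC. This stands in part: for serious events the weight of the text favours reporting, so a reader should not infer that every such event would be lost or would never reach the sponsor. It does not remove the explicit contrary sentence in 6.1.1, and it helps much less with non-serious events.

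A second defence uses the sentence just before the one at issue. It says that pre-existing conditions are "only considered adverse events if they worsen after starting the study treatment (any procedures specified in the protocol", which could make protocol procedures part of study treatment. That reading is possible. But the gloss sits in a sentence about pre-existing conditions, and it does not fit the section's own definition of an adverse event or either start date in Section 6. It does not resolve the conflict.

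Third, only 6.1.1 forbids recording outright. The Section 6 dates can be read as the window for all-cause collection, compatible with related-only collection earlier. The second 1.7 statement is a narrower rule that omits procedures. This is correct, and a claim that several sections each forbid recording would go too far.

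Finally, the cores are taken during the fiducial endoscopy, so attribution to the research sampling will not always be clear. That stands too. It is a reason to record such events and assess their cause.

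**Conclusion.** The contradiction is real and should be reconciled. Complications of the study-required biopsies before Cycle 1 Day 1 could go unrecorded if staff follow 6.1.1. This assumes only that staff might apply 6.1.1 as written.

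Three stronger readings are not supported.

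- **A number of missed events.** A reader might multiply the planned maximum of 12 + 15 = 27 treated patients by an assumed complication rate. The documents give no rate. The patients at risk are those biopsied, including any who never start immunotherapy, and some have two biopsies. The number at stake cannot be derived.
- **Bias in the safety results.** The Phase I and Phase II safety endpoints (1.4.1 and 1.5.1) count events on or after Cycle 1 Day 1 by definition. Neither they nor the immune-response endpoint changes.
- **A large prospective effect.** Enrolment closed on December 19, 2022. Patients not yet randomised were to enter Arm C, which Section 12.2 limits to 5, so a wording change can guide only the few patients who had not yet reached Cycle 1. For patients already biopsied, a listing can be only as complete as the records.

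**What to change.** Reconcile the provisions to Section 6.5.1 and the first 1.7 statement.

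- In 6.1.1, replace the sentence on events between consent and study treatment with:

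> From the first study-required procedure until Cycle 1 Day 1, AEs and SAEs considered related to a study procedure are recorded and reported; unrelated events are not.

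- Add the same exception to the 6.1.1 definition of an adverse event and to both the AE and the SAE start dates in Section 6. Changing the one sentence alone would leave the conflict in place for non-serious events.
- In the DLT and toxicity paragraph of 1.7, extend the rule to study procedures or treatment.
- In 6.2 and on the Appendix B form, allow relatedness to a study procedure.
- List any procedure-related events before Cycle 1 Day 1 separately from the 1.4.1 endpoint, whose window stays as it is.

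The cost is a few wording changes and one extra listing.
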